Title of Project:

Approach-Avoidance Conflict-a multi-level predictor for therapy response

Principal Investigator:

[name]. (LIBR) Principal Investigator, Laureate Institute for Brain Research Assistant Professor, University of Tulsa

Sponsor: Laureate Institute for Brain Research (LIBR)

ABSTRACT

Page ${\bf 1}$ of ${\bf 30}$

The aim of this study is to identify whether neural and behavioral responses related to the arbitration of conflicting avoidance and approach instincts can predict behavior therapy response for anxious and depressed individuals. This aim will be accomplished using behavioral and functional magnetic resonance imaging (fMRI) analysis pre and post behavioral therapy (BT). Research subjects will include treatment-seeking individuals with clinically significant symptoms of anxiety or unipolar depression. Diagnosis will be assessed using structured clinical interviews. Anxious and depressive symptom severity, personality characteristics, and general functioning will be collected via self-report paper-and-pencil questionnaires. Objective measures of approach, avoidance, and conflict behavioral responses will be collected using computer-administered testing and related neural responsivity will be measured using fMRI. This research has the potential to identify neural and behavioral approach-avoidance characteristics that can help predict which patients are likely to respond to standard behavior therapy for anxiety and depression (i.e., predictors of treatment effectiveness) and reveal targets for future treatment modifications.

A. SPECIFIC AIMS

The current study will accomplish the following aims:

Aim 1: Clarify the potential contribution of approach-avoidance behaviors and neural responses to anxiety and depression symptom severity.

Hypothesis 1.1: Approach-related behaviors and conflict arbitration behavior will explain a significant amount of variance in anxious and/or depressive symptoms, above and beyond avoidance-related behavior. **Hypothesis 1.2:** Activations within approach-related (i.e., striatum) and conflict arbitration (i.e., lateral PFC) neural circuitry will explain significant variance in anxiety and depressive symptom severity above and beyond activations within avoidance-related (i.e., amygdala) neural circuitry. Specifically, we expect increased levels of anxiety to relate to increased striatal responsivity while increased depression relates to reduced striatal responsivity.

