Anxiety and mood disorders are the most prevalent class of mental health disorders, with lifetime prevalence estimated at 32% and 18%, respectively^[1]. These disorders have tremendous personal and socioeconomic impacts (cost >\$1500 per-patient/year) due to days lost at work, increased health care utilization, and increased risk of mortality (e.g. cardiovascular disease)^[2-8]. First-line treatments for anxiety and depressive disorders include pharmacologic (e.g. SSRIs) and psychotherapeutic interventions (e.g. cognitive behavioral therapy [CBT] and behavioral therapy [BT]). While both are superior to placebo treatments, only 40-60% of patients experience significant improvement^[9-13] and 15-25% of responders relapse within one year^[12, 14-17]. Thus, we are producing long-lasting improvements in *less than 50% of patients*. This ineffectiveness has been moderately associated with symptom severity, illness duration, and comorbidity^[18-20] but these findings do not provide any strategies for improving treatment effectiveness. The current study will seek to identify behavioral or cognitive-affective predictors that indicate how well a patient is responding to treatment so that interventions can be further individualized to more effectively treat refractory patients.

Anxiety and Depressive Disorder Comorbidity

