- 10. Unwillingness or inability to complete any of the major aspects of the study protocol, including magnetic resonance imaging (i.e., due to claustrophobia), biopsy, blood draws, or behavioral assessment. However, failing to complete some individual aspects of these assessment sessions will be acceptable (i.e., being unwilling to answer individual items on some questionnaires or being unwilling to complete a behavioral task)
- 11. Non-correctable vision or hearing problems

Informed Consent

All participant interactions including consenting will be conducted in private interview/exam rooms. All subjects will be old enough to give informed consent (age 18 or older), and have all procedures fully explained to them. Care is taken to ensure the subject understands completely the IRB-approved consent form and that the form is appropriately endorsed with a signature as acknowledgement of his/her consent.

Participation Compensation

Participants will be compensated for their efforts during this study as follows:

- Completion of clinical, self-report, and behavioral assessment, estimated 7 hours total at both pretreatment and post-treatment and an additional 15 minutes per each of the 10 weeks of treatment): \$10 for every half hour, equating to a total of \$140 for completion of the pre-treatment session, \$140 for completion of the post-treatment session, and \$50 for 10 weekly assessments, for a total of \$330.
- Completion of self-report assessments, estimated at 30 minutes total at both 3 and 6 months following completion of treatment. These assessments will be completed online (via RedCAP) or via phone and therefore won't require an in-person session. To encourage completion of these follow-up questionnaires, participants will be provided \$20 compensation for each of these two time points (for a total of \$40).
- Completion of self-report assessments, estimated at 10-15 minutes, if they withdraw from the study prior to completion of treatment. These assessments will be completed online (via RedCAP) or via phone and therefore won't require an in-person session. Participants will be compensated \$10 for completion of these measures.
- Completion of MRI scanning (estimated 2.5 hours total, conducted at pre- and post-treatment): \$25/half hour, equating to a total of \$125 for completion of each MRI scanning session and a total of \$250.

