complete in total. Post-treatment self-report assessment is estimated to take a maximum of 3 hours total. Most assessments listed will be completed at both pre- and post-treatment sessions, except as follows. The PHQ-9 will only be used for screening purposes pre-treatment and will not be repeated. Even if the MINI was completed as part of previous LIBR studies or screening protocol, it will be repeated pre-treatment for the current study as well as post-treatment. The Life Chart Interview will be conducted in full at pre-treatment, but will only be updated at posttreatment (thus, decreasing the amount of time required to complete post-treatment assessments). If participants would like, they will be provided a summary chart of the important life events and mood ratings provided during the initial Live Chart Interview. The homework Rating Scale, Credibility Expectancy Questionnaire, and Working Alliance Inventory will only be conducted during weekly therapy sessions and the PROMIS Anxiety, PROMIS Depression, SDS, GAD-7, and the BADS will also be completed weekly (in addition to pre- and post-treatment) to assess severity of symptoms throughout the study protocol. At the 3 and 6-month online/phone followups, the PROMIS Anxiety, PROMIS Depression, SDS, BDI-II, OASIS, PSWQ, LSAS, PDSS, BADS, GAD-7, and the Treatment FollowUp Form will be completed. The Withdrawn Questionnaire, PROMIs Depression, PROMIS Anxiety, GAD-7, and SDS will be administered to individuals who withdraw from the study after beginning treatment. Those who withdraw from treatment will still be invited to complete the 3 and 6-month assessments. The questionnaires for those who withdraw and at the 3 and 6-month time points will be administered via phone or online (via RedCAP). In addition, the Health Anxiety Inventory[62] (modified for the current study, revised measure attached) and the Dimensional Obsessive—Compulsive Scale (DOCS)[63] may be given pre-treatment, 2-3 weeks throughout the therapy intervention, and at post-treatment and at the withdrawn timepoint. Participants who complete therapy interventions by videoconferencing technology will also be asked to complete the Telehealth Usability Questionnaire [64] (modified for the current study, revised measure attached).

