Stress & Self-Efficacy	NIH Toolbox Self-Efficacy Survey
Health Anxiety	Healthy Anxiety Inventory
OCD Symptoms	Dimensional Obsessive–Compulsive Scale (DOCS)
Telehealth	Telehealth Usability Questionnaire

These tasks will be conducted in private examination rooms and will be conducted via computer interface or verbally reported responses to the examiner. Some tasks will be completed in the MRI scanner; these tasks are identified in the descriptions below. All tasks will be completed at pre- and post-treatment assessment sessions. At the pre-treatment session, any task that has been completed within 2 weeks as part of any other research protocol at LIBR will not be repeated.

Approach-Avoidance Conflict Paradigms

AAC Task: The assessment of approach-avoidance conflict behavior will be conducted using the AAC task described in the "Preliminary Studies" section of this protocol except that points will be replaced with cents so that participants will be reward \$0-3 depending on their performance. The AAC task will last approximately 25 minutes and will be conducted once during an fMRI scan at baseline and repeated behaviorally post-treatment. This task will allow us to assess conflict-arbitration-related behavioral and neural processes.

Exploratory paradigm: This paradigm will assess for naturalistic exploratory approach and avoidance behavior by recording subjects' motor behavior when in a naturalistic setting (an office) filled with objects that invite exploration. This task is meant to mimic paradigms used in animal studies to quantify approach-avoidance behavior (open field tests) and will provide a more "real-world" task to complement the computer-based tasks.

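### Participants who stop therapy are assessed at withdrawal and at 3 and 6 months, but no contact is scheduled at the post-treatment time when completers are measured

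*Protocol*

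**What the plan says.** Protocol section E, Self-Report, sets out the contacts for people who do not finish therapy. At withdrawal: "The Withdrawn Questionnaire, PROMIs Depression, PROMIS Anxiety, GAD-7, and SDS will be administered to individuals who withdraw from the study after beginning treatment". The health anxiety and obsessive-compulsive scales may be added. After that: "Those who withdraw from treatment will still be invited to complete the 3 and 6-month assessments". The first sentence speaks of leaving the study and the second of leaving treatment; the text does not distinguish the two.

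Section D, Participation Compensation, agrees. The only item specific to withdrawers is "Completion of self-report assessments, estimated at 10-15 minutes, if they withdraw from the study prior to completion of treatment", done by phone or online and paid at $10. The same list pays for weekly assessments in each of the 10 treatment weeks. It times the later questionnaires as "estimated at 30 minutes total at both 3 and 6 months following completion of treatment".

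For behavioural measures, section E says: "All tasks will be completed at pre- and post-treatment assessment sessions". The Abstract describes the project as an analysis before and after therapy. Section F states that participants with GAD are randomised to BA or EXP.

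**The concern.** Completers have a self-report outcome at the end of the 10-week course. Those who stop have one at whatever week they stopped, and then at 3 and 6 months. No contact in their schedule is tied to the time at which completers are measured.

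This affects every aim that needs response or improvement with treatment: Aim 2 (predicting response), Aim 4 (improvement against blood markers), the functioning side of Aim 3, and Aim 5 (BA against EXP in GAD, the only randomised comparison). If those who stop fare worse than those who finish, response measured at post-treatment looks better than it is. For Aim 5 the error can run towards the hypothesis. Hypothesis 5.1 expects the two therapies to be equally effective, and if the less effective one also loses more of its poor responders, completer data make the two look more alike.

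A statistical analysis plan (SAP) can choose how to handle missing values, but it cannot create an observation that the protocol never schedules.

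**Working it through.** **Step 1. Trace the schedule for the four scales in the withdrawal pack** (PROMIS Anxiety, PROMIS Depression, GAD-7, SDS), from section E, Self-Report, and section D, Participation Compensation.

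| Time | Completer | Participant who stops therapy |
|---|---|---|
| Pre-treatment | yes | yes |
| Weekly, 10 weeks | yes | up to stopping; not stated afterwards |
| At withdrawal | not applicable | yes, at a variable week |
| Scheduled post-treatment | yes | no contact listed |
| 3 and 6 months | yes | invited |

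The 3- and 6-month contacts are counted from completion of treatment, a date that someone who stops does not have. Even these may therefore not line up with the completers' follow-up.

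**Step 2. Possible size on a continuous scale.** The protocol text gives no sample size, dropout rate, effect size or margin, so there is no stated figure to reproduce. All values below are assumptions. Let d be the share of an arm with no post-treatment score, and g the mean improvement of completers minus that of those who stop, in SD units.

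- All-starter mean = (1 − d) × completer mean + d × stopper mean, so completer mean − all-starter mean = d × g.
- One arm, d = 0.25, g = 0.5: 0.25 × 0.5 = 0.125 SD.
- Contrast between arms with the same g: bias = (d₂ − d₁) × g.
 - Dropout 15% against 25%, g = 0.5: 0.10 × 0.5 = 0.05 SD.
 - Dropout 10% against 30%, g = 0.8: 0.20 × 0.8 = 0.16 SD.
- With g = 0, both biases are zero whatever the dropout. With equal d and equal g, the contrast bias cancels but the one-arm bias stays.

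**Step 3. The same question as response rates.** Let p be the true response among all starters and q the response among those who stop. The completer rate is (p − d × q)/(1 − d). Section B says of existing treatments that "only 40-60% of patients experience significant improvement"; this is background, used here only to set a range for p.

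- p = 50%, q = 25%, d = 20%: (0.50 − 0.20 × 0.25)/0.80 = 0.45/0.80 = 56.2%. With d = 10% it is 52.8%, and with d = 30% it is 60.7%.
- If nobody who stops responds (q = 0), the three rates for d = 10, 20 and 30% are 55.6, 62.5 and 71.4%.
- Over p = 40 to 60% and d = 10 to 30%, the overstatement is 2 to 13 points when q = p/2, and 4 to 26 points when q = 0. It is zero when q = p.
- GAD comparison, true response 50% in both arms, dropout 10% in one and 20 or 30% in the other: a false difference of 3.5 or 7.9 points when q = 25%, and 6.9 or 15.9 points when q = 0.

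**The case against.** The strongest reply is that the schedule already follows these people well. The four scales are collected before treatment, weekly, at withdrawal and at 3 and 6 months. A longitudinal model over those scores can include everyone who started, with no completer-only analysis and nothing carried forward. The protocol states no completer-only analysis, and the method may be in an SAP that is not at hand. This stands: the figures above show what a completer-only analysis would do, not what the trial will do. It does not close the gap, because such a model must assume how those who stop would have scored at post-treatment, and the plan collects no observation at that time against which to check it.

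Some stronger readings are tempting and are not supported:

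- A reader might infer that the primary time point is lost. The protocol text names no primary outcome or time point; the weight on post-treatment follows from the pre/post design.
- A reader might infer that the missing people are the non-responders. That is plausible, but the document does not say it.
- A reader might infer that Aims 2, 3 and 5 are all fixed as pre-to-post change. Aim 2 speaks of treatment response and Aim 5 of effectiveness; only Aim 3 is worded as change.
- A reader might infer that a post-treatment contact is ruled out, or that weekly scales end with attendance. The text omits the first and is silent on the second. It also refers to a figure of the assessments that is not available here and cannot be counted for either side.

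**Conclusion.** The gap is real. As written, the plan gives those who stop therapy no contact at the time completers are assessed, so their self-report outcomes at that time will be missing. This can bias estimates of response (Aims 2 and 4, and the functioning side of Aim 3) if stopping is related to response. It can bias the BA against EXP comparison (Aim 5) if, in addition, the amount of dropout or its link to response differs between therapies.

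The illustrative bias of 0.05 to 0.16 SD in a completer-only contrast rests wholly on assumed dropout rates and gaps. The arm contrast concerns only the randomised GAD participants. The repeated scores that are collected soften the problem. This is a cheap improvement that the sponsor should make, not a flaw that invalidates the design.

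**What to change.** In section E, Self-Report, separate stopping therapy from leaving the study. Then add one contact: participants who stop therapy but keep consent are invited to complete PROMIS Anxiety, PROMIS Depression, GAD-7 and SDS by phone or online at their scheduled post-treatment (week-10) date, as well as the pack at withdrawal. Add a matching line to Participation Compensation at the $10 already paid for the withdrawal pack. State that these scores enter the outcome data for the randomised BA against EXP comparison. Leave their use in the other aims to the SAP, since a score taken off therapy may not be the right target for questions about response to therapy or its mechanism.

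The cost is one further contact of 10 to 15 minutes and $10 per person who stops; the forms and the remote route already exist. Uptake will be incomplete. The change cannot recover Aim 3's behavioural change scores, because the tasks are done only at the assessment sessions.

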In addition, participants will be provided the workbook, "Overcoming Depression One Step at a Time" [65] (http://www.amazon.com/Overcoming-Depression-One-Step-Time/dp/1572243678) for free, as a companion to the group therapy. Within this workbook are descriptions of the treatment rationale and the various exercises used during therapy, as well as handouts for them to use. In particular, there are activity charts they use to monitor their daily activities hour by hour (see attached measures). As an alternative to completing these charts on paper, they will be provided access to a web-based application developed by Laureate Institute for Brain Research. To use this application, they will create their own username and password and indicate their mood level associated with activities throughout the day. This information will then be accessible by the therapists, to help inform therapy. Those completing hard copies will be asked to bring their copies into treatment each week and a copy will be made for the purposes of research records.

Self-Report Measures		
DIAGNOSTIC AND DEMOGRAPHIC ASSESSMENT		
Diagnosis	MINI 6.0	
Demographics	Demographics and Psychosocial Form	
History	Assessment of Medical and Medication History	
Substance Use	Customary Drinking and Drug Use Record (CDDR)	
Handedness	Edinburgh Handedness Inventory	
Compliance	Medication Compliance History Questionnaire	
Compliance History	Therapy Compliance History Questionnaire	
Medical and Treatment Followup	Treatment Followup Form	
History	Life Chart Interview	

STANDARD SELF-REPORT SCALES	
Negative Valence	Symptoms of Depression Questionnaire (SDQ)
Negative Valence	Overall Anxiety Severity and Impairment Scale (OASIS)
Negative Valence	State Trait Anxiety Inventory (STAI)
Negative Valence	Anxiety Sensitive Index (ASI-3)
Negative Valence	Generalized Anxiety Disorder – 7 item (GAD-7)
Negative Valence	Intolerance of Uncertainty (IUS) Scale
Negative Valence	Penn State Worry Questionnaire (PSWQ)
Negative Valence	Liebowitz Social Anxiety Scale (LSAS)
Negative Valence	Panic Disorder Severity Scale (PDSS)
Negative Valence	Beck Depression Inventory-II (BDI-II)
Negative Valence	Patient Health Questionnaire – 9 (PHQ-9)
Negative Valence	Behavioral Activation Depression Scale (BADS)
Trauma	Traumatic Events Questionnaire (TEQ)
Trauma	Child Trauma Questionnaire (CTQ)
Positive / Negative Valence	Positive and Negative Affect Schedule (PANAS)

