Measures will be taken to help ensure treatment fidelity, according to previous recommendations^[106]. Each therapy session will be recorded and 40% of sessions will be randomly selected for fidelity ratings by research personnel. Skill acquisition and fidelity will be assessed using BT competencies developed for the Improving Access to Psychological Therapies (IAPT) Program^[107] (for exposure therapy) or the Quality of Behavioral Activation Scale (Q-BAS) for Behavioral Activation therapy, provided by [name]. These fidelity ratings will be made by experts in each therapy ([name], UCLA; and [name]; University of Wisconsin – Milwaukee), who will be provided de-identified audio tapes of therapy sessions via secure server access. Subject compliance will be assessed using (1) session attendance, (2) Homework Rating Scale^[108] to assess between-session compliance and (3) Vanderbilt Psychotherapy Process Scale (VPPS), therapist and client versions, to assess subject compliance and therapist behavior intra-session^[109]. The OASIS and PHQ-9 will be completed weekly to assess symptom severity. Each therapy session will be video and audio recorded and may be reviewed by the research team. The recordings will be destroyed by the end of the study, unless consent was given by ALL members in attendance at that group to use them for educational and training purposes (se consent form addendum).

Exposure Therapy for Treatment of Anxiety Disorders

Group-based, transdiagnostic therapy will be conducted according to a treatment manual developed by [name] at UCLA, which has been found effective in reducing anxiety symptoms for GAD, panic, and SAD^[110]. This 10-week protocol (one session per week, 90 minute sessions) will be modified to focus on exposure techniques, excluding cognitive restructuring. Exposure exercises will be individualized based on anxiety foci. For example, all subjects will complete initial interoceptive exposures. However, those with SAD may complete them while looking in the mirror, focusing on their ability to concurrently deliver a speech. For those with GAD, exposure to worry-related imagery will be a treatment focus. The specific manual to be used in this study is attached to this protocol.

Behavioral Activation Treatment of Patients with Depression

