BA is based on the premise that problems in an individual's life reduce their ability to experience reward from positive behaviors/events, leading to symptoms of depression. BA techniques focus on behaviorally stimulating reward activation in the subject by encouraging engagement in key aspects of life that are pleasurable or will ultimately make them feel productive. The BA sessions will occur once each week for 10 weeks (each 90 min). During the sessions the therapist and client will work together to develop reward activation assignments to be completed before the next session (i.e., in the subject's day to day life outside the therapist's office). The BA sessions will become highly individualized to target the behavioral patterns that cause depression in each subject. These behaviors will be identified early on in the sessions (first 1-2 sessions) and then subsequent sessions will consist of changing this behavior in order to stimulate feelings of reward, and thus alleviate symptoms of depression. The treatment will last 10 weeks (10 sessions, 90 minutes each) and will be conducted in accordance with the published clinician's guide on behavioral activation therapy^[102]. Each subject will be provided the workbook entitled "Overcoming Depression One Step at a Time: The New Behavioral Activation Approach to Getting Your Life Back"[65], which they will complete concurrently with the group therapy sessions.

G. GENDER/MINORITY/PEDIATRIC INCLUSION FOR RESEARCH

Women and minorities will be included in the study without prejudice according to their representation in the study population. Adult subjects will be recruited from the greater Metro Tulsa area and should thus share the racial and ethnic composition of this area. All efforts will be made to ensure that our subject population closely resembles the gender, ethnic and racial composition of the greater Tulsa area. Children are not included in this protocol due to its focus on understanding the neural systems underlying adult mood and anxiety disorders.

H. PARTICIPANT RISKS AND PLANS TO MINIMIZE RISKS

Risks Associated with Screening and Evaluation:

Risk: The risks and discomforts of the screening evaluations are minimal. Some of the questions in the interviews may be distressing or uncomfortable to answer due to their personal or emotionally relevant nature.

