The collection and processing of personal data from subjects enrolled in this study will be limited to those data that are necessary to fulfill the objectives of the study. Study consent records will be stored in the locked records room at the Laureate Institute for Brain Research. Only approved study personnel will have access to study records that contain any identifying information. Study data records and blood/urine/biological samples will be assigned code numbers and will not be individually identifiable. Code numbers are a combination of numbers and letters. Audio and video recordings will be destroyed after the study, unless consent was given by ALL members in attendance at that group to use the recordings for future educational and training purposes. The electronic data will be kept in a firewalled and password protected database on a secure server managed by Laureate Institute for Brain Research (LIBR). Vanderbilt University, with collaboration from a consortium of institutional partners, has developed a software toolset and workflow methodology for electronic collection and management of research and clinical trial data. REDCap (Research Electronic Data Capture) data collection projects rely on a thorough study-specific data dictionary defined in an iterative self-documenting process by all members of the research team with planning assistance from the information technology staff. The iterative development and testing process results in a wellplanned data collection strategy for individual studies. REDCap servers are housed in a local data center at Laureate Institute for Brain Research and all web-based information transmission is encrypted. REDCap was developed specifically around HIPAA-Security guidelines and is recommended to LIBR researchers by both our Privacy Office and the Western Institutional Review Board (WIRB). REDCap has been disseminated for use locally at other institutions and currently supports 240+ academic/non-profit consortium partners on six continents and over 26,000 research end-users (www.project-redcap.org). In addition, all subjects will be given the option of tracking their daily

Page 23 of 30

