activities and mood using a mobile web application (versus using the paper forms included in the Behavioral Activation workbook). Information collected by this application will be encrypted for transmission and for local (mobile client-side) and remote (the local data center at the Laureate Institute for Brain Research (LIBR)) storage. Authentication, audit and access controls will be implemented to ensure that only authorized users have access to the data and that all access is logged and monitored appropriately.

The Life Chart application, developed by LIBR, is accessed only within the LIBR network by participants and members of LIBR's research team. Life Chart data is stored behind a firewall through a password protected database on a secure server managed by LIBR that undergoes weekly security dynamic and static analysis scans through Veracode's platform under the HIPAA/Omnibus Act/HITECH/HITRUST policy. Veracode is used by over 2000+ companies in the world in making secure software (www.veracode.com).

The videoconferencing technology, GoToMeeting, utilizes encryption methods and meeting access control to avoid interception by anyone other than the invited participants. They have also implemented various mechanisms designed to address HIPAA privacy and security standards (see

https://www.gotomeeting.com/meeting/resources/hipaa-compliant-video-conferencing). However, all participants will be informed prior to using this technology that confidentiality of information shared during videoconferencing cannot be guaranteed.

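### Do participants in the exposure arm also receive the behavioral activation workbook and mood tracking?

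*Protocol*

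**What the plan says.** Four places bear on the point.

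- **Section E, Self-Report.** After the questionnaire schedule the text continues: "In addition, participants will be provided the workbook", a self-help book on depression supplied free alongside the group sessions. It adds: "Within this workbook are descriptions of the treatment rationale and the various exercises used during therapy, as well as handouts for them to use". Its activity charts may be kept on paper or replaced by a web application. On the application data: "This information will then be accessible by the therapists, to help inform therapy". On paper charts: "Those completing hard copies will be asked to bring their copies into treatment each week". No arm is named.
- **Data-handling text before the references.** A sentence that runs over a page break reads "In addition, all subjects will be given the option of tracking their daily" and then "activities and mood using a mobile web application (versus using the paper forms included in the Behavioral Activation workbook".
- **Section F, Behavioral Activation subsection.** "Each subject will be provided the workbook entitled", followed by the title of the same book, which is to be worked through in parallel with the BA sessions.
- **Section F, Exposure Therapy subsection.** "Group-based, transdiagnostic therapy will be conducted according to a treatment manual", with exposure techniques as its focus. It mentions no workbook, activity chart or application. The exposure manual is an attachment and is not part of the text at hand.

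Section F also states that people with GAD are randomised between EXP and BA. Aim 5 and Hypothesis 5.1 compare the two.

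**The concern.** The workbook is treatment content as well as a data form. It carries rationale and exercises, and therapists see the tracking entries. The nouns in section E and in the data-handling text cover both arms if taken at face value. Referring to group sessions does not settle the arm, because EXP is delivered in groups too. Just before the workbook paragraph, section E limits the telehealth questionnaire to people treated by videoconference, so one might expect a restriction here too if one were meant.

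If EXP participants did receive BA materials, the comparator in Aim 5 would be exposure plus part of BA. Aim 5 is the protocol's only randomised contrast. Reading one set of predictors for EXP and another for BA under Aim 2 would be less clean as well.

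**Working it through.** The protocol attaches no figure to this point, so the check is a comparison of texts.

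1. **Which arm does section E describe?** "Within this workbook are descriptions of the treatment rationale and the various exercises used during therapy, as well as handouts for them to use" holds only if the therapy in question is BA. Section F has this same book completed alongside BA sessions, while EXP follows its own manual built on exposure techniques. A depression workbook on activation does not contain the rationale or exercises of that exposure manual.

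2. **Whom does the data-handling sentence cover?** It offers the application as an alternative to the paper forms in the BA workbook. That choice is real only for someone who holds the workbook. The sentence sits in text on encryption and access control, hands the workbook to nobody, and does not define treatment.

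3. **Does the protocol use general nouns strictly?** No. The BA subsection says "Each subject will be provided the workbook entitled", and the exposure subsection likewise speaks of all subjects when it describes the opening interoceptive exercises. Neither can sensibly mean both arms. A general noun elsewhere is therefore weak evidence of a both-arm rule.

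4. **Is there a direct contradiction?** No sentence states that EXP participants receive the workbook, and none states that they do not. The apparent conflict comes from silence in the exposure subsection combined with a literal reading of two unqualified nouns.

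5. **Could a size be attached?** Only with assumed inputs. Let *d* be BA minus EXP in standard deviations, positive when BA is better.
   - If the materials add a benefit *c* to EXP, the observed difference is *d* − *c*. With *c* = 0.10 to 0.30, a true +0.30 becomes 0.30 − 0.10 = +0.20 down to 0.30 − 0.30 = 0.00. A true 0 becomes −0.10 to −0.30. A true −0.30 becomes −0.40 to −0.60.
   - If BA content displaces a fraction *f* of the contrast, the observed difference is *d* × (1 − *f*). With *f* = 0.10 to 0.40, +0.30 becomes 0.30 × 0.90 = +0.27 down to 0.30 × 0.60 = +0.18.

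   The contrast can shrink, vanish or grow according to values the protocol does not supply. The exercise supports no particular size or direction, and it applies only if the literal reading is the true one.

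**The case for a change.** The strongest opposing case is that intent is inferred and never written. The wording in the data-handling text is literally universal, and unlike the two subsections of section F it stands under no arm heading that would narrow it. An option to replace the workbook's forms, offered to everyone, can be taken to imply that everyone has those forms. Two members of staff, one working from section E and the other from section F, could in principle hand out different things. The fidelity ratings use a separate instrument for each therapy, and neither is described as checking for the other arm's materials.

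Part of this stands: the receiving arm is not named in section E or in the data-handling text, and the exposure manual cannot be consulted here. It does not follow that the content of the exposure arm is undefined. Section F is where the treatments are specified, it describes each arm separately, and section E's own account of the workbook agrees with it. A therapist running exposure groups from an exposure manual has no reason to issue a BA workbook because a questionnaire section omitted a qualifier.

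**Conclusion.** The wording is loose, but the plan does not need to change. Read together, the passages associate the workbook, its charts and the tracking application with BA, and nothing affirmatively gives them to the exposure arm. On that reading the randomised contrast in Aim 5 and the treatment-specific predictors in Aim 2 stand as described, and naming the arm in the two loose places would alter no comparison, analysis or result. It would be editorial tidying, suitable for whenever the text is next revised.

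The conclusion assumes that the unseen exposure manual does not itself include the workbook and that staff follow the arm-specific descriptions in section F. It takes no position on which materials either arm ought to receive. The size of any effect under the literal reading cannot be derived from the protocol.
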